9.2.15.1.7 THERASPHERE ADMINISTRATION DOCUMENTATION

Any technical problems or complications related to the delivery of TheraSphere treatment to the patient must be documented in the medical record. The details of any event and its impact on the patient should be documented on an Adverse Event eCRF. Patients in the Treatment group must certify continued eligibility prior to administration of TheraSphere. A new blood draw for labs and pregnancy and an ECOG Performance Status test should be performed within 48 hours of administration.

Using institutional practices, the activity of each vial of TheraSphere will be determined prior to administration. This activity will be used to calculate the actual dose delivered to the liver and lung which will be recorded on the appropriate eCRF.

Calculation of the liver dose (Gy) delivered:

Calculation of the delivered dose per infusion takes into account the activity lost to lung shunting plus activity associated with residual microspheres in the administration system and is provided by the following formula:

$$\text{Dose (Gy)} = \frac{50[\text{Injected Activity (GBq)}][1-F][1-R]}{\text{Mass of Selected Liver Target (kg)}}$$

where F = lung shunt fraction (determined in Section 9.2.14.1.3)
R = residual fraction (1-fraction of microspheres delivered)

Calculation of residual activity fraction for microspheres:

The fraction of microspheres remaining in the device is calculated using the following formula:

$$R = \frac{(W-b')}{(I-b)}$$

where R = residual activity fraction

b = background dose rate prior to source vial measurement

I = measured dose rate of source vial positioned greater than 30 cm from ionization chamber (or other measuring device)

b' = background dose rate prior to waste measurement and W = average dose rate of shielded waste container (containing discarded vial, microcatheter, tubing) positioned with center in same location as I

Calculation of Actual Lung Radiation Exposure:

Calculation of the lung dose (Gy) delivered in each infusion is provided by the following formula:

$$\text{Lung dose (Gy)} = 50 * \text{activity delivered (GBq)} * F$$

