⁴ Additional TS treatments may be administered only after progression if lesions are amenable to treatment

⁵ According to package insert at Weeks 1-4 for Control group patients and after all initial TS administrations for Treatment group patients only

⁶ Sorafenib to be stopped 7 days before subsequent TS administration on disease progression and restarted 2 weeks after TS is administered

⁷ If treatment commences within 14 days of randomization the clinical laboratory assessments are not required to be repeated.

⁸ The follow-up visits should be scheduled from the day of randomization. A window of ± 14 days is permissible from the scheduled date.

⁹ Progression of disease resulting in termination of further treatment

¹⁰ If available, ⁹⁹mTc-MAA SPECT or SPECT-CT taken as part of the TS planning and post TS treatment imaging (Y-90 SPECT-CT or Y-90 PET-CT or Y-90 PET-MRI) taken as part of the TS administration quality control, will be collected retrospectively for exploratory analysis

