9.1.3 PATIENTS RANDOMIZED TO THE TREATMENT GROUP

9.1.3.1 WEEKS 1-4 FOLLOWING RANDOMIZATION – TREATMENT GROUP

The following clinical patient management activities will be completed and documented on the electronic case report forms (eCRF):

1. If treatment commences greater than 14 days after randomization , complete appropriate clinical laboratory tests, including AFP, prior to treatment, as described in Section 0.
2. Conduct TheraSphere pre-treatment evaluations and administer TheraSphere in Treatment Group as described in Section 9.2.15.1.
3. Record details on the clinical assessments and administration of TheraSphere
4. Record any treatment and concurrent medications and any adverse events as described in Sections 9.2.18, 9.2.19 and 12.2.

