9.1.3.2 WEEKS 5-8 FOLLOWING RANDOMIZATION – TREATMENT GROUP

The following clinical patient management activities will take place and will be documented on the eCRF:

1. Complete appropriate clinical laboratory tests as described in Section 0.

2. Administer TheraSphere as described in Section 9.2.15.1.6 to the second lobe for patients in the Treatment Group with a bilobar treatment plan.
3. Record details on the clinical assessments and administration of TheraSphere
4. Record any treatments and concurrent medications and any adverse events as described in Sections 9.2.18, 9.2.19 and 12.2.

9.1.3.3 >2 & <6 WEEKS AFTER COMPLETE THERASPHERE TREATMENT

The following clinical patient management activities will take place and will be documented on the eCRF:

1. Administer SOC sorafenib in Treatment Group as described in Section 9.2.15.2.
2. Record details on the clinical assessments and administration of sorafenib.
3. Record any concurrent medications and any adverse events as described in Sections 9.2.18, 9.2.19 and 12.2.

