9.2.9 CLINICAL LABS

The following clinical laboratory assessments will be completed at study visits during the trial and must be documented as described in Section 13.4. Laboratory assessments undertaken as part of SOC clinical assessment may be used.

- Hematology: complete blood cell count (cBC) , differential white blood count (WBC), platelet count, hematocrit, hemoglobin,
- Coagulation: Prothrombin Time (PT), Partial Thromboplastin Time (PTT), International Normalized ratio for prothrombin time (INR)
- Chemistry panel: serum creatinine, blood urea nitrogen (BUN), glucose, aspartate aminotransferase (AST), alanine aminotransferase (ALT), albumin, amylase, lipase, total bilirubin, and alkaline phosphatase.

- Alpha-fetoprotein (AFP)

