9.2.10 PREGNANCY TEST

A serum pregnancy test for females of child-bearing potential will be performed at the screening visit. Patients determined to be pregnant are not eligible to participate in this clinical trial.

Female patients of childbearing potential must be advised that they should not become pregnant while participating in this clinical trial. Adequate methods of contraception must be used by these patients while they are enrolled in this clinical trial. Patients should not be breastfeeding while participating on this trial.

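### The 48-hour re-check before TheraSphere (labs, pregnancy test, ECOG) is waived or left out elsewhere in the protocol for the first two doses

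*Protocol*

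**What the plan says.** Protocol 9.2.15.1.7 sets the rule for every TheraSphere administration. "Patients in the Treatment group must certify continued eligibility prior to administration of TheraSphere", and then: "A new blood draw for labs and pregnancy and an ECOG Performance Status test should be performed within 48 hours of administration". No dose is exempted.

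Other places say something different or less:

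- **Schedule of Events, footnote 7**, attached to the hematology, coagulation and chemistry cells of the first TheraSphere column: "If treatment commences within 14 days of randomization the clinical laboratory assessments are not required to be repeated". SAP Table 2 carries the same footnote.
- **Section 9.1.3.1, item 1** (weeks 1-4, treatment group) repeats the waiver by asking for pre-treatment labs only under a condition: "If treatment commences greater than 14 days after randomization".
- **Section 9.1.3.2** (weeks 5-8), item 1: "Complete appropriate clinical laboratory tests as described in Section 0", with no time window. Item 2: "Administer TheraSphere as described in Section 9.2.15.1.6 to the second lobe for patients in the Treatment Group with a bilobar treatment plan".
- **Section 9.2.10**: "A serum pregnancy test for females of child-bearing potential will be performed at the screening visit". No later test is named.
- **Section 9.2.9** introduces its list with "The following clinical laboratory assessments will be completed at study visits during the trial". The list contains no pregnancy test.

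**The concern.** The re-check decides whether a patient still qualifies for a radioactive implant that cannot be withdrawn. Child-Pugh score, bilirubin, transaminases and pregnancy are all entry criteria (5, 11, 12, 42 and 43). Protocol 5.3 lists raised bilirubin and raised AST or ALT among the risk factors for serious events after TheraSphere.

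The second dose adds its own reason for fresh labs. Section 5.3 describes a cohort in which bilirubin rose after TheraSphere and, in most patients, returned to baseline in 4 to 6 weeks. The synopsis puts the second lobe typically 28 days (4 weeks) after the first, at the start of that recovery period.

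If sections disagree about which checks are due, sites could do different checks before the same dose. A site relying on footnote 7 would comply with the schedule and 9.1.3.1 but depart from 9.2.15.1.7, so deviations could not be classified consistently.

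**Working it through.** **Side-by-side reading.** Section 9.2.15.1.7 asks for all three checks, within 48 hours, at every dose. The remaining text gives:

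| Check | First dose | Second dose | Re-treatment |
|---|---|---|---|
| Labs | Marked in the schedule, but waived by footnote 7 and 9.1.3.1 if treatment starts within 14 days | Blank in the schedule; asked for by 9.1.3.2 item 1, no window | Marked, no window |
| Pregnancy test | Blank | Blank | Marked, no window |
| ECOG | Marked, no window | Marked, no window | Marked, no window |

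SAP Table 2 shows the same pattern. Because 9.2.9 does not list a pregnancy test, the requests for clinical laboratory tests in 9.1.3.1 and 9.1.3.2 do not bring one in.

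**Cross-references.** For the first dose, 9.1.3.1 item 2 points to 9.2.15.1, which includes 9.2.15.1.7. Section 9.1.3.4 does the same for re-treatment. For the second dose, 9.1.3.2 item 2 points only to 9.2.15.1.6, which does not contain the 48-hour rule. The second-dose pregnancy test is therefore the widest gap: the schedule, 9.2.10, 9.1.3.2 and the section it cites all omit it.

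**Age of results at dosing.** The plan states no figure to reproduce other than the 48 hours (2 days). Inputs, with randomization as Day 0:

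- screening tests: Day -14 to Day 0 (Protocol 9.1.1)
- footnote 7 limit: Day 14
- first dose: by Day 28 (synopsis, TheraSphere Treatment #1)
- second dose: weeks 5-8 (Protocol 9.2.15.1), that is Days 29 to 56

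Age of result = dosing day minus test day. For a site that follows the schedule alone:

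- labs at a first dose under footnote 7, maximum: 14 - (-14) = **28 days**
- pregnancy test at the first dose, maximum: 28 - (-14) = **42 days**
- pregnancy test at the second dose, minimum: 29 - 0 = **29 days**; maximum: 56 - (-14) = **70 days**

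The general visit allowance of plus or minus 14 days is not added.

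**The case against.** The strongest reply is that a site can satisfy every text simply by doing the tests, and that few sites would work from the schedule alone. Section 9.2.15.1.7 also holds the formulas for delivered liver dose, residual fraction and lung dose, which must be worked out per infusion and entered on the eCRF. A site therefore has to open that section for the second lobe too, whatever 9.1.3.2 cites. That makes it less likely that the rule is missed. It does not help with first-dose labs, where the reader of 9.2.15.1.7 meets a rule that footnote 7 and 9.1.3.1 contradict.

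Second, labs near the second dose are partly covered. Section 9.1.3.2 asks for them, and the week-8 follow-up labs fall on Day 56 plus or minus 14, Days 42 to 70, overlapping the dosing window of Days 29 to 56. But neither is tied to the dose, follow-up labs may come after it, and follow-up has no pregnancy test.

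Third, 9.2.10 requires contraception and advice against pregnancy, and the eligibility certification covers pregnancy in principle. These are real safeguards, but they do not replace a test that the protocol itself asks for. The pregnancy gap concerns women of childbearing potential only; the documents do not say how many were enrolled.

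Fourth, the 48-hour sentence says should rather than must, the figures of 28, 42 and 70 days are maxima, and nothing in the documents shows that sites did differ. All of that stands. The minimum of 29 days for the second-dose pregnancy test is not a worst case, however.

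Fifth, little can be changed prospectively. SAP 5.2.1 says all 520 patients were randomized before the first interim analysis. SAP 7.4 says the sample size was not increased and that patients still in follow-up had passed 40 months. This limits the benefit of an amendment; it does not remove the contradiction.

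**Conclusion.** The point holds. The protocol asks for fresh labs, a pregnancy test and ECOG within 48 hours of each TheraSphere dose, then waives the labs for an early first dose and omits the pregnancy test from the schedule at both initial doses. The schedule also omits labs at the second. ECOG is not missing; it lacks only the window.

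The schedule marks labs and pregnancy at re-treatment, so the protocol plainly regards these checks as appropriate before TheraSphere, and nothing explains why a first or second dose should need less.

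The size is up to 28 days for first-dose labs, up to 42 days for the first-dose pregnancy test and 29 to 70 days for the second, against 2 days. These figures assume an on-schedule patient at a site following the schedule alone; they are permitted ages, not observed ones. The matter is one of patient safety and consistent conduct and should be corrected.

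**What to change.** Amend the protocol as follows, with matching changes to SAP Table 2:

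1. Remove footnote 7 from the first TheraSphere column, leaving it on the control-arm sorafenib column only.
2. Have 9.1.3.1, 9.1.3.2 and 9.2.10 require labs, a serum pregnancy test (women of childbearing potential) and ECOG in the 48 hours before each TheraSphere administration, with results reviewed before dosing. The present wording does not say on which side of the dose the 48 hours lie.
3. Point 9.1.3.2 item 2 to 9.2.15.1 rather than 9.2.15.1.6.
4. Mark labs and pregnancy in the first and second TheraSphere columns, and add the 48-hour window there and to the re-treatment and ECOG cells.

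The cost is a wording and schedule correction plus a few extra blood draws at sites that now use the waiver. Nothing is added that 9.2.15.1.7 does not already ask for.

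If initial dosing is complete, produce instead a listing of days from the last labs and ECOG to each TheraSphere dose. The dates are among the eCRF items in SAP 8.6.1. That list includes no pregnancy-test date, so that part would need another eCRF field or source records.

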9.2.15.1.8 THERASPHERE POST-TREATMENT PATIENT MANAGEMENT

Immediately following treatment, the patient should remain under observation consistent with institutional SOC guidelines for aftercare in procedures involving femoral or brachial artery catheterization. These aftercare guidelines are unique and subject to the policies and procedures dictated by the respective radiology and radiation safety departments at each institution. Prophylactic treatment using gastric inhibitor (H2 blocker) should continue for 14 – 21 days post treatment. In addition, steroids (e.g., Medrol Dose Pack) may be taken (with food) over the first six days post-treatment.

Prior to discharge, patients should be instructed regarding after-care and provided with a 24-hour telephone number that they may use to contact the Site Investigator if they develop a problem or have questions about their treatment.

Any concurrent medication or therapy deemed necessary, including gastric prophylaxis, to provide adequate supportive care to the patient in the post-treatment period may be administered according to institutional standard of clinical care and should be documented on the Concurrent Medications eCRF.

9.2.15.1.9 RADIATION SAFETY IN THE IMMEDIATE POST-TREATMENT PERIOD

Special radiation isolation procedures for Treatment group patients are not necessary following TheraSphere Treatment. The existence of a small amount of long-lived radioactive byproducts in TheraSphere is a function of the production method¹³: The predominant by-products are Y-91, Y-88 and Cr-51 with respective half-lives of 59, 107 and 28 days. The 3 year accumulated dose to the patient's liver is estimated to be 1/1000 of the planned treatment dose.

Should a patient die or require surgery in the period immediately following-TheraSphere treatment the hospital radiation safety officer should be consulted. At 60 days after the TheraSphere calibration date, a surgeon explanting a treated liver in a procedure lasting one hour would be exposed to an estimated dose to the hands of <0.6 mrem. This is similar to estimated background doses from natural radiation sources which range from 0.5 to 0.8 mrem/day. Institutional radiation safety guidelines for handling of the body and/or body tissues should be followed.

9.2.15.2 SOC SORAFENIB TREATMENT

All patients will receive SOC treatment with sorafenib in accordance with the package insert. Special attention should be paid to patients with hypertension or prolonged QT or at risk of developing QT prolongation (patients with a congenital long QT syndrome, patients treated with a high cumulative dose of anthracycline therapy, patients taking certain anti-arrhythmic medicines or other medicinal products

that lead to QT prolongation, and those with electrolyte disturbances such as hypokalemia, hypocalcemia, or hypomagnesemia). Blood pressure monitoring plus electrocardiogram with magnesium and calcium laboratory tests done at screening and first post-therapy visit then every 6-8 weeks are recommended. Abnormal results or adverse events related to these conditions observed in study subjects should be recorded as adverse events. Therapies used to manage such adverse events should be recorded in the Concomitant Medication eCRF

Dosage adjustments and drug holidays will be determined to be in the patient's best interest at the discretion of the physician. Consider discontinuing sorafenib if QT/QTc increases over 500ms or increases to 60ms above the baseline reading. All dosage adjustments must be logged on the Treatment Medication eCRF.

Caution is recommended when considering concomitant administration of the following medications; please consult the sorafenib summary of product characteristics/prescribing information for details:

- Warfarin, phenprocoumon or CYP2B6, CYP2C8 and CYP2C9 substrates (monitor regularly for changes in prothrombin time, INR or episodes of clinical bleeding)
- Inducers of metabolic enzymes such as rifampicin, St. John's wort, phenytoin, carbamezepine, phenobarbital, dexamethasone may increase sorafenib metabolism and decrease sorafenib concentrations
- UGT1A1 or UGT1A9 pathways metabolized compounds due to glucuronidation inhibition

Control group patients will start SOC sorafenib therapy as soon as possible after randomization.

Treatment group patients should initiate the SOC sorafenib regimen at least 2 weeks after the completion of TheraSphere administration, and generally from 2 to 6 weeks following completion of TheraSphere administration.

For Patients in the Treatment group who have initiated SOC sorafenib treatment and have progression with hepatic lesions amenable to further TheraSphere treatment, sorafenib should be discontinued seven (7) days prior to the administration of each subsequent TheraSphere treatment. If considered medically appropriate, SOC sorafenib therapy may be resumed after TheraSphere administration, but should only be resumed at least 2 weeks after TheraSphere has been administered.

Sorafenib should be discontinued from seven (7) days prior through 48 hours after each angiographic procedure to reduce the risks of bleeding.

9.2.16 EFFICACY IMAGING – CT/MRI

Baseline efficacy imaging scans will be obtained during screening. Efficacy assessment scans will be taken in accordance with SOC clinical management guidelines every 8 weeks post randomization until death. Most patients will be evaluated by CT images. MRI images are also permitted. The imaging modality used at baseline must continue to be used for all efficacy images throughout the study. Duplicate DICOM images will be submitted to the sponsor or designee to permit future Central Imaging Review in accordance with image submission instructions.

Triple Phase Spiral CT abdomen – must be performed with cuts of 10 mm or less in slice thickness contiguously in the axial plane. From these images, hepatic and extra-hepatic lesions will be read according to the RECIST criteria v1.1 (Appendix 3).

Spiral CT chest and pelvis – must be performed with cuts of 10 mm or less in slice thickness contiguously in the axial plane. From these images, extra-hepatic lesions will be read according to the RECIST criteria v 1.1 (Appendix 3).

For Secondary Study Endpoints based on radiographic assessment, the investigator will identify, read and measure hepatic lesions for size at Baseline using RECIST v 1.1 criteria. At all subsequent follow-up visits, the images (using the same modality) will be read and measured and compared back to the Baseline images and then categorized as Complete Response, Partial Response, Stable, or Progressing at each time point using RECIST v 1.1 (Appendix 3). These data will be captured on the eCRF and may be summarized showing tumor response over time.

The tumor response, according to the mRECIST criteria and based on a blinded centralized independent imaging assessment, will be recorded as an exploratory endpoint. Investigators will not be required to perform mRECIST assessments.

[REDACTED]

[REDACTED]

[REDACTED]

[REDACTED]

[REDACTED]

[REDACTED]

9.2.18 STUDY TREATMENT MEDICATION RECORD

The administration of treatment during the trial will be recorded throughout the trial on the appropriate eCRF. Start/stop dates, dates of change of dosage, and any drug holidays will be recorded.

9.2.19 CONCURRENT MEDICATION RECORD

At every study visit new medications or changes in concurrent medications will be documented on the appropriate concurrent medication eCRF. Documentation will include dosage, start/stop dates, date of change of dosage and any drug holidays.

9.2.20 STUDY COMPLETION

Patients complete the trial upon reaching the primary efficacy endpoint of death. A patient may also decide he/she no longer wishes to participate in the trial. In accordance with the Declaration of Helsinki, and applicable state and federal regulations, a trial subject has the right to withdraw from the study at any time and for any reason. Every effort should be made to have patients complete the study within the provisions of informed consent. However, the participation of the patient may be discontinued at any time during the study when, in the judgment of the investigator, sponsor or subject, it is appropriate.

The reasons for study completion include:

- Death of the patient
- Patient's desire for any reason to withdraw consent
- Administrative reasons
- It is considered necessary by the investigator or sponsor, for any reason

Lost to follow-up is not an adequate reason for withdrawal. Patients should be encouraged to attend study visits until completion of the study or until a decision is taken to withdraw for one of the above-noted reasons.

If intolerance to the study treatment, the patient should be under medical supervision as long as deemed appropriate by the treating physician. Similarly, if study treatment is discontinued due to an AE, the event will be followed until it resolves to the Investigator's satisfaction or is considered stable. The details and reasons for discontinuation must be carefully and completely documented. In either situation, the patient must be followed-up for survival until one of the reasons for study completion is met.

